## 7. EVALUATION OF SAFETY AND MANAGEMENT OF TOXICITY

### 7.1 SAFETY PARAMETERS

#### 7.1.1 ADVERSE EVENTS

An adverse event (AE) is defined as any unfavorable and unintended change in the structure, function, or chemistry of the body, or worsening of a pre-existing condition, temporally associated with the use of a product whether or not considered related to the use of the product. In this study, such changes will be monitored, classified, and summarized, as Clinical or Laboratory AEs. Medical condition/diseases present before starting the investigational drug will be considered adverse events only if they worsen after starting study treatment. Throughout the course of the study, all solicited and unsolicited AEs will be monitored and reported on an AE CRF, including the event's seriousness, severity, action taken, and relationship to investigational product(s). AEs should be followed until resolution or stable and the outcome will be documented on the appropriate CRF. All AEs should be recorded in standard medical terminology rather than the subject's own words.

AEs include the following:

- Pre- or post-treatment complications that occur as a result of protocol mandated procedure during or after screening (before the administration of study drug).
- Any pre-existing condition that increases in severity, or changes in nature during or as a consequence of the study drug phase of a human clinical trial, will also be considered an AE.
- Complications of pregnancy (e.g., spontaneous abortion, miscarriage, ectopic pregnancy, fetal demise, still birth, congenital anomaly of fetus/newborn); see [Section 7.1.9](#) for additional information.
- AEs that occur from the study screening visit onwards and throughout the duration of the study, including the follow-up off study drug period will be recorded as an AE.
- Conditions that lead to a medical or surgical procedure.

AEs do not include the following:

- Medical or surgical procedures (e.g., surgery, endoscopy, tooth extraction, transfusion) performed as a result of an AE.
- Pre-existing diseases or conditions or laboratory abnormalities present or detected before the screening visit that do not worsen.
- Situations where an untoward medical occurrence has not occurred (e.g., hospitalization for elective surgery, social and/or convenience admissions).

- Overdose without clinical sequelae.
- Any medical condition or clinically significant laboratory abnormality with an onset date before the informed consent form is signed is not an AE. It is considered to be pre-existing and will be documented on the medical history CRF.
- Uncomplicated pregnancy.
- An induced elective abortion to terminate a pregnancy without medical reason.

### 7.1.2 SERIOUS ADVERSE EVENTS

A serious adverse event (SAE) is any AE that meets one of the following conditions:

- Death during the period of surveillance defined by the protocol;
- Is immediately life-threatening (e.g., subject was, in the view of the Investigator, at immediate risk of death from the event as it occurred). This does not include an AE that, had it occurred in a more serious form, might have caused death;
- An event requiring inpatient hospitalization or prolongation of existing hospitalization during the period of protocol defined surveillance (including any overnight stay in the hospital, regardless of the length of stay, even if the hospitalization is only a precautionary measure to allow continued observation). However, hospitalization (including hospitalization for an elective procedure) for a pre-existing condition that has not worsened, does not constitute an SAE;
- Results in persistent or significant disability/incapacity or substantial disruption of the ability to conduct normal life functions;
- Results in congenital anomaly or birth defect;
- An important medical event that may not result in death, be life threatening, or require hospitalization, but based upon appropriate medical judgment, may jeopardize the subject and may require medical or surgical intervention to prevent one of the outcomes listed above. Examples of such medical events include 1) allergic bronchospasm requiring intensive treatment in an emergency room or at home, 2) blood dyscrasias or convulsions that do not result in inpatient hospitalization, 3) the development of drug dependency or drug abuse or 4) the development of a malignancy;
- Is medically significant or requires intervention to prevent one or other of the outcomes listed above.

### 7.1.3 CLARIFICATION OF SERIOUS ADVERSE EVENTS

- Death is an outcome of an AE, and not an adverse event in itself.
- The subject may not have been on investigational medicinal product at the occurrence of the event.
- Dosing may have been given as treatment cycles or interrupted temporarily before the onset of the SAE, but may have contributed to the event.
- “Life-threatening” means that the subject was at immediate risk of death from the event as it occurred. This does not include an event that might have led to death if it had occurred with greater severity.
- Complications that occur during hospitalizations are AEs. If a complication prolongs the hospitalization, it is an SAE.
- Inpatient hospitalization means that the subject has been formally admitted to a hospital for medical reasons, for any length of time. This may or may not be

overnight. It does not include presentation and care within an emergency department nor does it include full day or overnight stays in observation status.

The investigator will attempt to establish a diagnosis of the event on the basis of signs, symptoms, and/or other clinical information. In such cases, the diagnosis will be documented as the AE and/or SAE and not the individual signs/symptoms.

Serious adverse events that are ongoing should be followed until resolution or are clinically stable. The reporting period for SAEs is described in [Section 9.5](#).

#### 7.1.4 EVENT REPORTING FOR DISEASE PROGRESSION OR EXCLUSIONARY HISTOLOGIC FINDINGS POST-STUDY TREATMENT

After starting study treatment, if there is histologic confirmation of progression of HSIL to microinvasive or invasive squamous cell carcinoma, the event must be reported as an SAE. For the finding of carcinoma, subjects should be managed per routine standard of care (i.e. surgical excision), discontinued from study treatment but continue on study without further biopsy. Post-study treatment histologic diagnosis of adenocarcinoma-in-situ or adenocarcinoma should also be reported as an SAE. In both instances the condition for SAE reporting should be categorized as a medically important event unless another criterion is met.

#### 7.1.5 UNEXPECTED ADVERSE DRUG REACTIONS AND EXPEDITED REPORTING

An adverse drug reaction (ADR) is any noxious and unintended responses to a medicinal product related to any dose, for which a causal relationship between a medicinal product and an adverse event is at least a reasonable possibility; i.e., there is evidence to suggest a causal relationship between the product and the adverse event. An unexpected ADR is one, the nature or severity of which is not consistent with the applicable product information (investigator's brochure, protocol, and user manual). Reports that add significant information on specificity or severity of a known, already documented SAE constitute unexpected events. For example, an event more specific or more severe than described in the Investigator's Brochure or protocol would be considered "unexpected." Specific examples would be (a) acute renal failure as a labeled ADR with a subsequent new report of interstitial nephritis and (b) hepatitis with a first report of fulminant hepatitis.

The Sponsor will assess each serious ADR report for expectedness, to determine if it is a serious unexpected suspected adverse reaction (SUSAR) which requires prompt reporting to regulatory authorities and participating investigators as an expedited report, according to the applicable regulatory requirements. Additional occurrences of the SUSAR will be required to be reported on an expedited basis until the applicable product information is amended.

In addition to single-case reports of SUSARs, the Sponsor shall notify regulatory authorities and participating investigators of information that might materially influence the benefit-risk assessment of a medicinal product, sufficient to consider changes in product administration or overall conduct of a clinical investigation. Examples of such information include a clinically important increase in the rate of occurrence of a serious expected adverse event, the identification of a significant hazard to the subject population, or a major safety finding from a study conducted in animals.

### 7.1.6 UNANTICIPATED (SERIOUS) ADVERSE DEVICE EFFECT (UADE)

Unanticipated adverse device effect means any serious adverse effect on health or safety or any life-threatening problem or death caused by, or associated with, a device, if that effect, problem, or death was not previously identified in nature, severity, or degree of incidence in the investigational plan or application (including a supplementary plan or application), or any other unanticipated serious problem associated with a device that relates to the rights, safety, or welfare of subjects.

Per the definition above, a UADE is a type of serious adverse event (SAE) that requires expedited reporting on the part of the sponsor. As a reminder, all SAEs regardless of relationship to device, drug or procedure are to be reported to Sponsor by the study investigator within 24 hours. Sponsor will assess each device related SAE to determine if anticipated based on prior identification within the investigational plan.

### 7.1.7 ASSESSING SEVERITY (INTENSITY)

Adverse events should be captured once on the CRF at the maximum severity reported. The investigator will grade laboratory AEs and clinical AEs with respect to the following levels of severity as per Common Toxicity Criteria for Adverse Events (CTCAE) v 4.03 for applicable subject populations:

- Mild (Grade 1)
- Moderate (Grade 2)
- Severe (Grade 3)
- Potentially Life Threatening (Grade 4)
- Death (Grade 5)

The investigator will grade injection site reactions in accordance with September 2007 FDA Guidance for Industry—Toxicity Grading Scale for Healthy Adult and Adolescent Volunteers Enrolled in Preventive Vaccine Clinical Trials.

### 7.1.8 CASUAL RELATIONSHIP OF CLINICAL MATERIAL TO ADVERSE EVENTS

A causally related AE is one judged to have a reasonable possibility of a relationship to the administration of the IP and/or the investigational device. An AE may also be assessed as not related to the IP and/or the investigational device. Because the investigator is knowledgeable about the subject (e.g., medical history, concomitant medications), administers the IP, and monitors the subject's response to the IP, the investigator is responsible for reporting adverse events and judging the relationship between the administration of the IP and device and a subsequent AE. The investigator is aware of the subject's clinical state and thus may be sensitive to distinctions between events due to the underlying disease process versus events that may be product related and may have observed the event. The Sponsor will assess the overall safety of the IP delivered by EP and determine whether to report expeditiously to the regulatory agencies.

Investigators should use their knowledge of the subject, the circumstances surrounding the event, available site and non-site laboratory and clinical records, and an evaluation of any potential alternative causes to determine whether or not an adverse event is considered to be related to the IP and/or the investigational device indicating "yes" or "no"

accordingly. Causality should be assessed by the investigator as “yes, related” or “no, unrelated” by the following criteria:

- Yes – there is a reasonable possibility that administration of the Study Treatment contributed to the event;
- No – there is no reasonable possibility that administration of the Study Treatment contributed to the event and there are more likely causes.

The following guidance should also be taken into consideration:

- Temporal relationship of event to administration of IP and/or the investigational device;
- Course of the event, considering especially the effects of dose reduction, discontinuation of IP, or reintroduction of IP (where applicable);
- Known association of the event with the IP, EP or with similar treatments;
- Known association of the event with the disease under study;
- Presence of risk factors in the Study Subject or use of concomitant medications known to increase the occurrence of the event

#### 7.1.9 ABNORMAL LABORATORY VALUE

Laboratory abnormalities are usually not recorded as AEs or SAEs. However, laboratory abnormalities (e.g., serum chemistry, CBC, CPK, urinalysis) independent of the underlying medical condition that require medical or surgical intervention or lead to IP interruption or discontinuation must be recorded as an AE, or SAE, if applicable. In addition, laboratory or other abnormal assessments (e.g., electrocardiogram, x-rays, vital signs) that are associated with signs and/or symptoms must be recorded as an AE or SAE if they meet the definition of an AE (or SAE) as described in [Section 7.1](#). If the laboratory abnormality is part of a syndrome, record the syndrome or diagnosis (e.g., anemia) not the laboratory result (e.g., decreased hemoglobin).

Any laboratory abnormality that is new in onset or worsened in severity or frequency from the baseline condition and meets one of the following criteria will be recorded as an AE:

- Requires therapeutic intervention or diagnostic tests
- Leads to discontinuation of study treatment
- Has accompanying or inducing symptoms or signs
- Is judged by the investigator as clinically significant

#### 7.1.10 POST-TRIAL REPORTING REQUIREMENTS

All AEs and SAEs including deaths, regardless of cause or relationship, must be reported for subjects on study (including any protocol-required post-treatment follow-up).

Investigators are not obligated to actively seek AEs or SAEs beyond the follow up period for subjects. However, if the investigator learns of an AE or SAE that occurs after the completion or termination visit and the event is deemed by the investigator to be related to the study treatment, he/she should promptly document and report the event to the study team and medical monitor.

#### 7.1.11 PROCEDURES FOR DOCUMENTING PREGNANCY DURING STUDY

Subjects who are pregnant or expect to become pregnant during the course of the study up to 6 months following the last study treatment of investigational product will be excluded

from participation in the study. Should a subject become pregnant after enrolling in the study, she will not be given any further study treatments. A Pregnancy Form will be completed by the site personnel and submitted to the sponsor within 24 hours after learning of the pregnancy. Site personnel will submit the Pregnancy Form to the Sponsor as described in [Section 7.4.2](#).

The investigator will also report this event to the IRB within 24 hours of becoming aware of the pregnancy. Sites must request the subject's permission to query pregnancy outcome and follow each subject to determine the outcome of the pregnancy. Results will be summarized in the clinical study report (CSR).

Subjects who become pregnant at any point during the study will continue to be followed for safety assessments without receiving further study treatment. Procedures that are contraindicated during pregnancy, including additional treatments, must not be performed. Investigators should use clinical judgment regarding subsequent study-related blood collection based on the presence or absence of anemia in each subject. Subjects who are not withdrawn will continue to be followed for safety assessments to study discharge per protocol.

All pregnancies that occur from the time of first study treatment through the follow up visits must be reported. The investigator will monitor the subject and follow the outcome of the pregnancy. If the end of the pregnancy occurs after the study has been completed, the outcome will be reported directly to the study team and the medical monitor.

## 7.2 METHODS AND TIMING OF COLLECTION OF SAFETY DATA

Non-serious AEs and SAEs will be collected for each subject from the time when informed consent is obtained through Week 100.

The sources of AEs cover:

1. The subject's response to questions about her health (a standard non-leading question such as 'How have you been feeling since your last visit?' is asked at each visit).
2. Symptoms spontaneously reported by the subject.
3. Evaluations and examinations where the findings are assessed by the investigator to be clinically significant changes or abnormalities.
4. Other information relating to the subject's health becoming known to the investigator (e.g. hospitalization).

All AEs will be reported on the appropriate CRF. Any SAE occurring during the course of the study must be reported to the sponsor within 24 hours of awareness.

## 7.3 SAFETY AND TOXICITY MANAGEMENT

The Medical Monitor will be responsible for the overall safety monitoring of the study.

Safety assessments include the following:

- Incidence of all adverse events classified by system organ class (SOC), preferred term, severity, and relationship to study treatment
- Changes in safety laboratory parameters (e.g., hematology, serum chemistry, and urinalysis)

- Local and systemic injection site review; special attention will be paid to the examination of the injection site. Administration site reactions and the subject's complaints will be documented

### 7.3.1 ADVERSE EVENTS OF SPECIAL INTEREST

Adverse events of special interest (AESI) are the adverse events deemed related to VGX-3100 delivered with CELLECTRA® 2000 that require expedited communication from the site to the Sponsor and meet any of the following criteria:

- Grade 3 or greater persistent administration site erythema, and/or induration recorded  $\geq 2$  hours immediately after Study Treatment
- Grade 4 or greater persistent administration site pain, tenderness recorded  $\geq 2$  hours immediately after Study Treatment
- Grade 3 or greater fever
- Grade 3 or greater systemic symptoms, including generalized pruritus
- Grade 3 or greater laboratory abnormalities

As per the Toxicity Grade for Healthy Adults. The most severe grade for that particular event is to be documented in the CRFs.

Sites will inform the Sponsor of an AESI within 24 hours via method described in [Section 7.4.2](#), to discuss whether further dosing should continue.

### 7.3.2 STOPPING RULES (CRITERIA FOR PAUSING OF STUDY)

If any of the following situations occur then further enrollment and Study Treatments will be halted immediately until a thorough investigation has been conducted by the Medical Monitor and Principal Investigator and the IRB/EC (if applicable):

- One third or more subjects experience an AESI assessed as related to Study Treatment;
- Three or more subjects in the same treatment arm discontinue due to an AE related to the Study Treatment;
- Any subject experiences an SAE (or potentially life threatening AE or Grade 4 AE) or death assessed as related to Study Treatment;
- Two or more subjects within a treatment arm experience the same or similar grade 3 or 4 adverse event, assessed as related to Study Treatment;
- Four or more subjects across all treatment arms experience the same or similar grade 3 or 4 adverse event, assessed as related to Study Treatment;
- Any report of anaphylaxis assessed as related to Study Treatment.

Upon conclusion, the sponsor or designee will notify all investigators and IRBs/EC (if required) regarding the outcome of any investigation stemming from a Study Pause.

Guidelines for assessing relatedness are detailed in [Section 7.1.8](#).

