- If any SAE (or potentially life-threatening AE) or death assessed as related to study treatment occurs, further enrollment and study treatment will be halted immediately until a thorough investigation has been conducted by the Medical Monitor, Principal Investigator for the trial, IRB (if applicable) and the DSMB.
- If three or more subjects in this study experience the same Grade 3 or 4 adverse event, assessed as related to study treatment, further enrollment and study treatment will be halted immediately until a thorough investigation has been conducted by the Medical Monitor, Principal Investigator for the trial, and the DSMB.
- In the event of two identical, unexpected, Grade 4 toxicities, assessed as related to study treatment, further enrollment and study treatment will be halted immediately until a thorough investigation has been conducted by the Medical Monitor, Principal Investigator for the trial, IRB (if applicable) and the DSMB.

The sponsor or designee will notify all investigators and IRBs/EC (if required) regarding the outcome of any investigation stemming from a Study Pause.

Immunogenicity Assessment: The study will explore humoral and cell mediated immune responses to VGX-3100, and VGX-3100 with imiquimod, in blood samples taken at baseline (both Screening as well as Day 0 prior to dosing) and at Weeks 15, 27, 48, 74 and 96. Vulvar samples will also be analyzed for evidence of immune responses at Screening and at Weeks 48, 74 and 96.

Virologic Assessment: Tissue samples will be obtained to characterize HPV infection at Screening, Week 48, 74 and 96. Cervical samples, oropharyngeal rinse samples, vaginal, and intra-anal tissue swab samples will be obtained to characterize HPV infection in samples from study subjects taken at Screening (cervical sample only), Day 0 prior to dosing (OP, vaginal and intra-anal only) and at Weeks 27, 48, 74, and 96.

If there is residual tissue in the paraffin block after histologic diagnoses have been rendered, then unstained slides and/or the relevant paraffin blocks will be collected for immunohistochemistry (IHC) and in situ hybridization (ISH) for the presence of HPV-16/18. Whenever possible, these studies will be performed on tissue sections from the diagnostic biopsy (pre-dose) and from tissue obtained post-dose (Week 48, 74 and 96).

HLA haplotyping: A sample from one time point during the study will be tested to explore the relationship between subject HLA haplotypes and regression.

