#### 3.3.1 DATA SAFETY & MONITORING BOARD

An independent Data Safety & Monitoring Board (DSMB) will provide safety oversight. The DSMB will meet quarterly to review safety data. The DSMB will be charged with advising the Sponsor if there appears to be a safety issue. No formal interim analysis is planned. The following stopping rules will be applied:

- If at any time during the study one-third (1/3) or more of the subjects experience an Adverse Event of Special Interest, further enrollment and study treatment will be halted immediately until a thorough investigation has been conducted by the Medical Monitor, Principal Investigator for the trial, and the DSMB.
- If any SAE (or potentially life-threatening AE) or death assessed as related to study treatment occurs, further enrollment and study treatment will be halted immediately until a thorough investigation has been conducted by the Medical Monitor, Principal Investigator for the trial, IRB (if applicable) and the DSMB.
- If three or more subjects in this study experience the same Grade 3 or 4 adverse event, assessed as related to study treatment, further enrollment and study treatment will be halted immediately until a thorough investigation has been conducted by the Medical Monitor, Principal Investigator for the trial, and the DSMB.

- In the event of two identical, unexpected, Grade 4 toxicities, assessed as related to study treatment, further enrollment and study treatment will be halted immediately until a thorough investigation has been conducted by the Medical Monitor, Principal Investigator for the trial, IRB (if applicable) and the DSMB.

The sponsor or designee will notify all investigators and IRBs/EC (if required) regarding the outcome of any investigation stemming from a Study Pause.

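### Versions 1.0 and 1.1 carry two different study-pause lists with no stated precedence, and Section 10.4.1 asks the DSMB for a comparison with a placebo group the trial does not have

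*Protocol*

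**What the plan says.** **Synopsis and Section 3.3.1 (versions 1.0, 1.1 and 1.2).** Four rules are stated as mandatory. The one at issue reads "If three or more subjects in this study experience the same Grade 3 or 4 adverse event, assessed as related to study treatment"; the count is over the whole study and the event must be the same one. Under this rule the halt stays in force "until a thorough investigation has been conducted by the Medical Monitor, Principal Investigator for the trial, and the DSMB". The synopsis repeats the threshold: "If three or more subjects in this study experience the same Grade 3 or 4 adverse event".

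**Section 7.3.2 (versions 1.0 and 1.1).** Six rules are listed, also as mandatory. The matching one reads "Two or more subjects within a treatment arm experience the same or similar grade 3 or 4 adverse event", assessed as related, with a companion rule at four or more subjects across arms. Two triggers have no counterpart in 3.3.1: "Three or more subjects in the same treatment arm discontinue due to an AE related to the Study Treatment" and "Any report of anaphylaxis assessed as related to Study Treatment". Enrollment and dosing are "halted immediately until a thorough investigation has been conducted by the Medical Monitor and Principal Investigator and the IRB/EC (if applicable"). The DSMB is not named.

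**Section 10.4.1 (versions 1.0 and 1.1).** The DSMB is to advise the sponsor on safety, and also if regression under VGX-3100 looks too low relative to placebo. Sections 8.1 and 8.2 describe an open-label trial with two arms, both receiving VGX-3100, and Section 8.9 tests each arm against a fixed 2%.

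**Version 1.2.** The supplied text ends at Section 6.12. Its contents list still shows 7.3.2 and 10.4.1, but their wording cannot be read.

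**The concern.** A pause rule works only if everyone who may have to apply it reads the same threshold. Here a site or board member who opens Section 3.3.1, the section titled for the DSMB, finds a looser list with no pointer to the stricter one. That reader would not pause for two same-arm cases of the same related Grade 3 event, for similar but not identical Grade 3 events, for three related discontinuations in an arm, or for a related anaphylaxis that was neither serious nor potentially life-threatening.

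The exit condition differs as well. A related SAE is on both lists, but only 3.3.1 makes a DSMB investigation a condition for resuming. For the triggers found only in 7.3.2, no visible text requires one.

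The placebo wording is a separate fault: it gives the board a comparison that it cannot make.

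**Working it through.** No figure in the plan needs reproducing. The check sets the rules side by side and then counts.

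| Item | Synopsis and 3.3.1 | 7.3.2 |
|---|---|---|
| Related Grade 3/4 event, repeated | 3 subjects study-wide, same event | 2 in one arm, or 4 across arms, same or similar event |
| Related SAE, potentially life-threatening AE, or death | any | any, with Grade 4 named |
| AESI | one third of subjects | one third of subjects, related |
| Two identical unexpected related Grade 4 events | listed | covered by the any-Grade-4 rule |
| Related discontinuations | none | 3 in one arm |
| Related anaphylaxis | only if serious or potentially life-threatening | any |
| DSMB investigates | yes | not named |

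**Which differences matter.** The AESI rules are equivalent, because 7.3.1 defines an AESI as related. Section 7.1.7 labels Grade 4 as potentially life-threatening, so one related Grade 4 event already pauses the study under both lists. The count conflict is therefore about Grade 3.

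**Where the counts disagree.** Let a be the number of affected subjects among 24 on VGX-3100 alone and b the number among 12 on the combination, all with the same event. Section 3.3.1 needs a + b ≥ 3. Section 7.3.2 needs a ≥ 2, or b ≥ 2, or a + b ≥ 4. Over every pair (a, b), the lists differ only at (2, 0) and (0, 2), where 7.3.2 pauses and 3.3.1 does not. No pair triggers 3.3.1 alone. Three subjects in two arms always put two in one arm, so the four-across-arms rule never fires first. For the same reason, three subjects with similar but not identical events always meet the 7.3.2 count and not the 3.3.1 count.

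**How often two events split the lists.** Given exactly two affected subjects among 36 at equal risk:

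P(same arm) = [C(24,2) + C(12,2)] / C(36,2) = (276 + 66) / 630 = 0.543.

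Equal risk is an assumption. If the odds of the event in the combination arm are θ times those in the other arm, the share is (276 + 66θ²) / (276 + 66θ² + 288θ). It equals 0.543 at θ = 1. Its minimum is at θ = √(276/66) = 2.05, where it is 269.9 / (269.9 + 288) = 0.484, using 2√(276 × 66) = 269.9. So whatever the odds ratio, the lists split in at least 48% of such cases.

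**A concrete case.** Table 9 lists severe injection-site pain as a less common reaction. It is not an AESI at Grade 3, because the criterion in 7.3.1 is "Grade 4 or greater persistent administration site pain, tenderness recorded". Two related Grade 3 cases in one arm halt the study under 7.3.2 and leave it running under 3.3.1.

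**Placebo reference.** The only non-VGX-3100 benchmark in the plan is the 2% historical rate. At a true rate of 2%, the chance of no responder among 24 is 0.98^24 = 0.62. Even the worst possible result would be unremarkable against 2%, so that rate cannot show that regression is too low.

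**The case against.** The strongest reply is that the lists do not clash in operation. Both are mandatory, every 3.3.1 trigger is also a 7.3.2 trigger, and the stricter list sits under the heading devoted to stopping rules. That stands: a reader might infer that the sections give instructions that cannot both be followed, and they do not. The fault is that nothing tells a user of 3.3.1 that a stricter list exists.

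Second, other safeguards remain. Section 4.3.1 has the medical monitor and PI discuss further treatment after a related Grade 3 toxicity, and 7.3.1 requires notice of an AESI within 24 hours. These are real, but they concern one subject and do not pause enrollment or other subjects' dosing.

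Third, one might read the DSMB's absence from 7.3.2 as exclusion. The documents do not support that. Section 10.4.1 provides for ad hoc meetings, lets the Chair recommend suspension, and leaves procedures to a charter that is not supplied. What can be said is that no visible text makes a DSMB investigation a condition for lifting a pause triggered only by 7.3.2.

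Fourth, the inconsistency is verified only in versions that 1.2 has superseded. This limits the claim. The version 1.2 change summary names only the removal of a questionnaire and calls the rest administrative. That makes carry-over plausible but does not show it.

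**Conclusion.** The point holds as an internal inconsistency in versions 1.0 and 1.1 that should be corrected. The thresholds, event wording, triggers and conditions for resuming differ between two mandatory lists, and no precedence is stated. For the repeated Grade 3 rule, the lists split in 54.3% of cases in which exactly two of 36 subjects share the event at equal risk. This measures how often one list pauses when the other does not; it is not a measure of harm, and the documents give no event rate from which to size harm.

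The placebo charge in 10.4.1 is wrong on its face. A reader might infer that it affects the efficacy conclusion, but no formal interim analysis, threshold or test depends on it.

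For version 1.2, the synopsis and 3.3.1 rules are confirmed unchanged. Nothing is concluded about its 7.3.2 or 10.4.1.

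**What to change.** 1. Read 7.3.2 and 10.4.1 in version 1.2 and confirm whether the wording persists.
2. Make 7.3.2 the single governing list, with one event wording (either the same event, or the same or a similar event), and state whether expected Grade 3 injection-site pain counts.
3. In the synopsis and 3.3.1, replace the restated rules with a cross-reference to 7.3.2.
4. Name the DSMB in every pause investigation, and align its charter.
5. Delete the placebo-comparison charge from 10.4.1. Do not substitute the 2% historical rate, for the reason shown in the working.

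The cost is amendment wording and charter alignment, with no change to sample size, visits or analysis. The downside is somewhat more frequent pauses for anyone who had applied only 3.3.1, including for expected Grade 3 injection-site pain unless it is exempted.
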